General Overview of Procedures. All potential participants will undergo an initial phone screening interview, via telephone or in person. The initial screening will include questions regarding pain, age, and additional health history information to ensure that no exclusion criteria are present. Those who meet study inclusion criteria will also be screened for COVID-19 using the COVID-19 phone screening form. If still eligible, participants will be scheduled for an individual baseline assessment during which informed consent will be reviewed, medical and demographic history will be obtained to ensure eligibility, questionnaires will be administered, and a physical performance battery will be conducted to examine lower extremity function. At the completion of the baseline assessment, eligible participants will be scheduled for a 7-week program (90 min/session) in which participants' complete activities designed to enhance hope, positive affect, pain acceptance, and self-efficacy. Participants will complete weekly home activities and will be asked to bring the home assignments into each session. Participants can miss only one session without making it up or up to two sessions if made up with individual sessions in person, over the phone, or using a PHI Zoom call. Given evidence that intervention effects on pain and psychological outcomes in older adults are strongest when delivered using group-based approaches (relative to an individual format) (22), we have chosen to administer our protocol via groups.

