Cognitive Testing. The Montreal Cognitive Assessment (MoCA) (25) is a widely used screening assessment for detecting cognitive impairment. It was validated in the setting of mild cognitive impairment and has subsequently been adopted in numerous other settings clinically. Participants with scores <26 will be excluded from participation as this could interfere with completion of the study intervention. The alternative/Equivalent version of the MoCA (Version 7.2) will be used to decrease possible learning effects when the MoCA (Version 7.1) has been administered within the past 3 months of study participation. This will serve as a safeguard for test-retest effects for participants who may have recently participated in studies requiring the administration of this instrument.

Physical Performance Battery. The Back Performance Scale (BPS) (26) consists of five tests (i.e., sock test, pick-up test, roll-up test, fingertip-to-floor test, lift test) to assess mobility-related activities in individuals with back pain. Each test is scored from 0 to 3, and a total summed score ranging from 0 to 15 is computed (higher scores equal worse functioning).

Sessions 2-8 (Intervention Delivery):

Intervention Procedure. All sessions will be administered by the PI, Co-I, and/or interventionist (masters/PhD level psychologists). Due to COVID-19, intervention sessions (Week 1 – Introduction and Background through Week 7 – Review of Skills and Wrap-Up) may be delivered online through PHI Zoom. To standardize the application of the intervention and ensure treatment fidelity, the resilience intervention is manualized and includes interventionist and client workbooks with materials and handouts for discussion. Client workbooks are written at the 6th grade reading level as measured by Flesh-Kinkaid Grade Level estimates. These intervention workbooks have been reviewed in an earlier phase of this trial (ARIAA 2A), whereby we conducted semi-structured focus groups and key informant interviews with approximately 47 older adults with cLBP to provide feedback on the treatment manual (IRB201802729). Interventionists will be provided with a checklist of procedures specific to each session, and each checklist will be reviewed to ensure treatment adherence. Participants who miss a group visit will be allowed to complete an individual make-up session, with the stipulation that only two missed sessions will be permitted.

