in-session activities, and assignment of homework. The intervention will be comprised of the following activities. **Week 1: Introduction and Background.** Participants will be provided with instruction on group therapy guidelines (e.g., confidentiality, respect, privacy), an overview of the purpose and structure of the program, and rationale for the use of resilience-enhancing activities for the management of cLBP. Participants will also be given education on cLBP etiology and symptoms and provided the opportunity to discuss their own personal experiences associated with chronic pain. As a home exercise, participants will be asked to complete a character strengths survey. **Week 2: Pleasant Activities.** During the second session, participants will be given instruction on how to increase the number of pleasant events in their life and will be provided with a list of pleasant activities to choose from (31). For their home practice, participants will be encouraged to engage in three pleasant activities over the week and to record things they are grateful for. **Week 3: Pain Acceptance.** Participants will receive instruction on valued activity, psychological flexibility, and mindfulness-based exercises for enhancing pain acceptance and awareness. A values assessment will be administered to assist participants in identifying important values in their life (32). **Week 4: Hope and Goal-Setting.** Based on Snyder's theory of hope (27), participants will focus on their personal strengths and learn ways in which to create attainable goals through the development of pathways and agency thinking. Participants will be asked to develop a goal that they would like to achieve over the course of the intervention to facilitate hopeful thinking and goal-directed behavior, and to identify areas in their life that inspire hope (33). **Week 5: Positive Events and Reappraisal.** To increase attentional focus on positive events, participants will be taught ways in which to minimize the impact of adverse events and to downregulate negative emotions and thoughts through positive reappraisal (34). As a home-based activity, participants will be encouraged to record, at minimum, one positive event that occurred every day, as well as negative events in which they had to practice positive reappraisal (35). **Week 6: Pain Self-Efficacy.** While it is anticipated that self-efficacy will gradually be fostered throughout the course of the intervention (i.e., skills mastery experiences, feedback on progress, social persuasion through group support), this session will complement ongoing training by targeting problem-solving skills and confidence building, as well as empowering participants to promote adaptive pain management behaviors. Participants will be asked to engage in diaphragmatic breathing as a form of relaxation and to note areas of accomplishment over the course of the intervention (36, 37). **Week 7: Review of Skills and Wrap-Up:** Skills learned in the previous sessions will be reviewed and specific plans for maintenance of resilience activities will be discussed. Participants will also complete post-treatment outcome questionnaires and provide feedback on the intervention program.

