Statistical Methods. The goal of the study will be to target 50 participants for the pilot intervention. Accounting for a conservative 20% attrition rate, we will recruit an additional 10 participants (Total $N=60$). This sample size is feasible and will provide stable estimates of dropout rates, feasibility, and acceptability of the intervention protocol. We anticipate screening an additional 70 participants who may not meet eligibility criteria (i.e., screen failures). **Data Analysis: Specific Aim 1.** The analysis of feasibility, tolerability, and acceptability outcomes will be predominantly conducted with descriptive statistics, with means and standard deviations reported. To assess feasibility, we will calculate a ratio between participants enrolled versus the number of participants commencing treatment. Tolerability will be examined by measuring completion rates (i.e., participants completing all seven sessions of the intervention). Participant acceptability of the intervention will be assessed through treatment credibility ratings and satisfaction with the program (59). Chi-square tests and between-group t -tests will be used to compare group differences in baseline characteristics between completers and participant dropouts. **Specific Aim 2.** To assess change in primary study outcomes (i.e., pain severity, pain interference, negative affect, quality of life), mean differences from pre- to post-intervention will be calculated using paired samples t -tests. Clinical significance of treatment changes will be determined by identifying participants whose raw change score for each outcome variable is greater than one-half of a standard deviation from their baseline score (60, 61). Using residualized change scores (i.e., difference between the post-intervention value with the pre-intervention score covaried out), Pearson correlations will be computed to examine associations between outcome and treatment target change scores.

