Confidentiality. All trained personnel assisting with the study will be instructed on the importance of protecting participants' confidentiality and will have successfully completed the required education on protection of human research participants. All paper and computer records will be identified only by subject number rather than by name. All study records will be stored in locked file cabinets and will only be available to the PI or other project staff. Computer data files (without subject identifiers) will be stored on computer servers with secure passwords and electronic storage devices will be encrypted. All study records will be stored in locked file cabinets and will only be available to the PI or other project staff. Study staff will be instructed to not record any information (e.g., responses to back pain criteria) obtained during the phone screen. Each intervention group will be audio-recorded (and video-recorded via Zoom) for the evaluation of therapist adherence to the protocol, and a random selection of 50% of all sessions conducted will be reviewed by the study PI and Co-I. No identifying information will be transcribed as the purpose of this digital recording is to assess treatment integrity. Once the audio recordings are reviewed and adherence is discussed with the study therapist, the recordings will be destroyed. Prior to destruction, the recordings will be kept in a locked filing cabinet in the laboratory of the PI. Video recordings via Zoom will only be used to extract an audio file, and video files will be promptly destroyed after each intervention visit.

8. Possible Discomforts and Risks: The risks for this study are minimal and appropriate safeguards are planned and in place to handle risks in a timely and appropriate manner.

Protection against potential risks:

Physical Performance Exam. The back performance test may cause participant discomfort as a result of the exam. The examiner will monitor the response of participants in order to gauge the need to discontinue the exam. Participants may stop at any time.

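### The Aim 2 paired t-tests take no account of therapy groups, and no route is stated for obtaining post-treatment forms from people who stop

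*Combined protocol and SAP*

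**What the plan says.** **Delivery.** Section 7, General Overview of Procedures, says that "we have chosen to administer our protocol via groups", citing evidence that effects in older adults are strongest in that format. Under Intervention Content, the Week 6 text lists "social persuasion through group support" among the ways self-efficacy should build up. The Confidentiality text ("Each intervention group will be audio-recorded") shows that there is more than one group. The size and number of groups are not given.

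**Analysis.** Statistical Methods, Specific Aim 2, names pain severity, pain interference, negative affect and quality of life as its primary outcomes. For these, "mean differences from pre- to post-intervention will be calculated using paired samples" t-tests. The document contains no therapy-group term, ICC, mixed model or robust standard error. It also contains no definition of the Aim 2 analysis set and no missing-data method.

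**Data collection.** At Week 7, "Participants will also complete post-treatment outcome questionnaires and provide feedback on the intervention program". Study Questionnaires lets some Visit 1 and Visit 8 forms be completed at home, to spread the burden. Absence is limited (Intervention Procedure: "only two missed sessions will be permitted"), and the Participants text lets the principal investigator decide whether a new pain treatment leads to exclusion. Neither place says whether post-treatment forms are then sought or analysed. Dropouts enter the analysis only through a comparison of baseline characteristics with completers.

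**Numbers.** The target is 50. "Accounting for a conservative 20% attrition rate, we will recruit an additional 10 participants", for a total of 60. Aim 1 separately reports "a ratio between participants enrolled versus the number of participants commencing treatment", so loss before the first session is counted on its own.

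**The concern.** There are two separate problems.

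*Precision.* A paired t-test assumes that one participant's change is independent of another's. The protocol itself gives a reason to expect members of a group to change together. If they do, the standard error is too small. The mean change is not biased by this.

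*Mean change.* A paired test needs both values. Unless people who stop return post-treatment forms, the test covers only those who stayed long enough to give them. The planned comparison of completers with dropouts uses baseline characteristics, so it cannot show whether those lost changed less.

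The abstract presents the results as a platform for future intervention research. What is at stake is an effect estimate carried into the next trial with too narrow an interval or from a favourable subset.

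**Working it through.** **1. The plan's own figure.** 50 x 1.20 = 60, as stated. At 20% loss, 60 x 0.80 = 48 have both values, and 48 is used below. (Dividing instead gives 50 / 0.80 = 62.5, or 63. That is a separate matter.)

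**2. Clustering.** Group size m and ICC are not in the documents, so they are assumed. The design effect for the mean change is DE = 1 + (m - 1) x ICC, and the true standard error is about sqrt(DE) times the one the t-test reports. The type I error of the unadjusted two-sided 5% test comes from simulation: 20,000 runs per setting, n = 48, in 8, 6 or 4 groups. The unequal layouts keep the same average size.

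| m | ICC | DE | sqrt(DE) | Type I error, equal groups | Type I error, unequal groups |
|---|---|---|---|---|---|
| 6 / 8 / 12 | 0 | 1.00 | 1.00 | 4.7 / 4.9 / 4.8% | 4.9 / 4.9 / 4.8% |
| 6 / 8 / 12 | 0.01 | 1.05 / 1.07 / 1.11 | 1.02 / 1.03 / 1.05 | 5.8 / 5.8 / 6.3% | 5.8 / 6.0 / 6.1% |
| 6 / 8 / 12 | 0.05 | 1.25 / 1.35 / 1.55 | 1.12 / 1.16 / 1.24 | 7.9 / 9.2 / 11.2% | 8.2 / 9.6 / 11.5% |
| 6 / 8 / 12 | 0.10 | 1.50 / 1.70 / 2.10 | 1.22 / 1.30 / 1.45 | 11.2 / 12.9 / 18.3% | 11.3 / 14.1 / 18.1% |

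The effect is nil at ICC 0 and negligible at 0.01.

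**3. Missing post-treatment values.** Let s be the share of starters with no post value and d their assumed mean change. The observed mean is assumed to be 0.40 baseline SD, with positive meaning improvement. Starter mean = (1 - s) x 0.40 + s x d.

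The 20% attrition applies to the 60 recruited, and some of those lost may never start. So 12 of 60 is the upper end for starters. If 6 never start, s = 6/54; if 9 never start, s = 3/51.

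| d | s = 12/60 | s = 6/54 | s = 3/51 |
|---|---|---|---|
| -0.5 | 0.220 | 0.300 | 0.347 |
| 0 | 0.320 | 0.356 | 0.376 |
| 0.2 | 0.360 | 0.378 | 0.388 |
| 0.4 | 0.400 | 0.400 | 0.400 |
| 0.6 | 0.440 | 0.422 | 0.412 |

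With no change in those lost, the overstatement is 0.40/0.320 = 1.25 (25%), 0.40/0.356 (12.5%) or 0.40/0.376 (6%). At d = 0.2 it is 11%, 6% or 3%. At d = 0.4 it is nil. At d = 0.6 the reported value is 9%, 5% or 3% too low. If those lost got worse the gap is larger: 0.40/0.220 = 1.82 in the extreme cell. With 10 lost (the stated target of 50) and no change, the starter mean is 0.333 (20%) if all had started and 0.364 (10%) if half never start.

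**4. The interval for the starter mean.** If d is a fixed constant, only the first term varies, so the interval is (1 - s) times the one for the observed mean. If d is tied to the data, d = observed mean + delta, the starter mean is observed mean + s x delta and needs the full width. Shrinking it there is wrong. With 12 of 60 missing, equal true change and ICC 0, the shrunken interval from a random-group model misses the truth 7.1-7.9% of the time, against about 5% for the plain t-test. For groups of 6 its half-width is 0.8 x 0.340 = 0.272 SD of change, narrower than the t-test's 0.29.

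**5. Cost of a random-group model.** The 95% half-width is 0.29 SD of change for the t-test. For the model with equal groups of 6, 8 or 12 it is 0.34, 0.36 or 0.41 at ICC 0, and 0.37, 0.41 or 0.52 at ICC 0.05. Power for a change of 0.40 SD of change at ICC 0 falls from about 78% to 65%, 60% or 52%. The model's type I error stayed at 2.8-5.7% in every setting, but it estimated the group variance as zero in 38-39% of runs even at ICC 0.05.

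Steps 3 and 5 use different units (baseline SD and SD of change). They cannot be compared without a pre-post correlation, which the documents do not give.

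**The case against.** The other side has good points.

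- Feasibility and acceptability are the primary aim (section 6). No alpha, power or efficacy rule is stated, and the sample size is justified by dropout, feasibility and acceptability. A type I error figure therefore illustrates the loss of precision; it is not a decision error in this trial. This stands.
- The clustering harm is uncertain, while the loss of power from a random-group model is certain. This stands against making the model the headline, not against showing it.
- With unequal groups, that model estimates a weighted mean rather than the participant mean. This stands and should be stated.
- The protocol has safeguards: individual make-up sessions, a $60 payment for Session 7, and a 3-month online assessment of pain, mood and quality of life. These may limit loss, but the text does not say that people who stop receive the post-treatment or 3-month forms.

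Some stronger readings are tempting but unsupported. A reader might infer that Aim 2 is a completers-only analysis. The plan does not say so: completing all seven sessions is its tolerability measure, and a paired test takes anyone with both values. A reader might take 20% as the loss among starters, but Aim 1 counts non-starters separately. A reader might also infer that participants who begin new pain treatments must be handled in one particular way. That is a choice of question, and the documents do not settle it.

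**Conclusion.** The point holds in limited form. The independence assumption conflicts with the way treatment is delivered, and the plan states neither whose post-treatment data enter Aim 2 nor how they are obtained from people who stop.

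The size depends on figures that are not in the documents. For groups of 6 to 12 and 48 analysed, the precision problem runs from nothing at ICC 0 to a true error rate of 11-18% at ICC 0.10. Overstatement of the mean is 6-25% if lost starters do not change, depending on how many had started. It is zero if they change equally, reversed if they do better and larger if they worsen.

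A reader might infer that the trial would reach a false efficacy conclusion. The documents do not support that: Aim 2 is exploratory in a single-arm pilot, and the risk is a poor estimate taken forward. Obtaining the forms is the more urgent half, because they cannot be recovered reliably later.

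**What to change.** 1. Send the existing post-treatment questionnaires, by REDCap or on paper, to everyone who attended at least one session, except those who withdraw consent. Include all data obtained in the Aim 2 analysis. Cost: a short protocol and IRB change, and some staff contact.
2. Keep the paired t-test. Beside it, as a sensitivity analysis, report a confidence interval from a model of change scores with a random therapy-group effect and Satterthwaite or Kenward-Roger degrees of freedom, together with group sizes and the ICC of change. State that with unequal groups the model estimates a weighted mean, and that with few groups its interval is wider even at ICC 0. Cost: SAP wording and one model per outcome.
3. For values still missing, report a range for the starter mean, with every outcome scored so that positive is improvement. Run the assumed mean in those lost from 0.5 SD worsening, through no change and the observed mean, to 0.2 SD above it. Multiply the interval by the share observed only where the assumed mean is a fixed constant (0.5 SD worsening, no change). Use the full width where it is tied to the observed mean.

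Results with and without participants who began new pain treatments may be added as an optional report.
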